15.1 Schedule of Events

	Screening ^a	D1	D4	D8	D15	D29	D91	D181 (EOS)	ET Visit	Unscheduled Visit for Suspected COVID19	Unscheduled COVID-19 Convalescent Visit
Window	D-14 to -1	0	±1	±1	±3	±3	±5	±7	NA	NA	NA
Visit	1	2	Phone	3	4	5	6	7	NA	NA	NA
Informed consent	X										
Inclusion/exclusion	X										
Reassess study vaccine eligibility ^b		X									
Demographics	X										
Medical history (including vaccination history)	X										
Pregnancy test ^c	X	X									
CCI											
Physical examination ^f	X	X		X	X	X	X	X	X	X	X
Vital sign measurements ^g	X	X		X	X	X	X	X	X	X	X
Viral screening assays ^h	X										
Hematology and serum chemistry ^h	X	X ^d		X							
CCI											
Group assignment for Part A/ Randomization for Part B		X									
CCI											
Initiate eDiary for solicited AEs ⁱ		X									
12-lead ECG examination	X			X							
Site staff review of eDiary			X	X							
CCI											
COVID-19 assessment ^k									X ^k	X ^k	

Note: Due to the ongoing pandemic, follow-up visits may be completed via telephone calls, consistent with local regulations.

- a. If the investigator believes there is a reasonable justification to do so, all screening procedures may be repeated (maximum 1 rescreening per participant is allowed). Only results from the rescreening visit, if it occurs, will be taken into consideration and recorded in the eCRF. The participant can only be vaccinated once the investigator receives the results and confirms the eligibility criteria.
- b. Prior to study vaccine administration, participants will be reassessed for development of any new condition that would be considered exclusionary including acute illness or pregnancy. Assessment will be based on pregnancy test results, participant-reported symptomology, vital sign measurements, and physical examination findings.
- c. A serum pregnancy test will be performed at screening in WOCBP. A urine pregnancy test by dipstick will be performed prior to study vaccination. Negative confirmation is required prior to study vaccine administration. Pregnancy test may be repeated at an unscheduled visit per investigator's discretion.
- d. On day 1, the blood sample should be collected *before* study vaccine administration.
- e. **CCI**
[REDACTED]
- f. A complete physical examination including height and weight will be performed at screening. Symptom-directed physical examinations will be performed as clinically indicated at subsequent visits.
- g. Vital sign measurements (temperature, pulse rate, oxygen saturation by pulse oximetry, respiration rate, and blood pressure) should be collected before and after study vaccination on D1. Vital sign measurements should be performed before any scheduled blood collection. Participants who are febrile (temperature $\geq 38.0^{\circ}\text{C}$ or $\geq 100.4^{\circ}\text{F}$) before study vaccination on D1 should be rescheduled for study vaccination within the relevant window period.
- h. Clinical safety laboratory testing will include hematology and serum chemistry. Screening laboratory tests may be repeated once for enrollment requirements. At unscheduled visits, clinical safety laboratory testing may be performed per investigator's discretion. Viral screening assays include HIV1/2 Antigen/Ab, hepatitis B surface antigen (HBsAg) and hepatitis C virus antibodies (HCV Abs). Testing for HCV RNA will be performed in participants who test positive for HCV Ab.
- i. An eDiary will be initiated for daily recording by the participant of solicited local and systemic adverse events.
- j. Solicited local and systemic AEs will be collected during the 7 days after study vaccination via eDiaries. Unsolicited AEs will be collected for 28 days after study vaccination. SAEs, MAAEs, and AESIs will be collected for the duration of the study.
- k. All suspected cases of COVID-19 in study participants will be diagnosed and clinically evaluated according to the definitions provided in Section 6.1.2. Such participants may have unscheduled study site visits and nasopharyngeal RT-PCR testing for SARS-CoV-2. An unscheduled visit may be performed for participants reporting symptoms consistent with COVID-19. An initial visit should be scheduled upon report of symptom onset, preferably within 3 days of symptom onset. Alternatively, an investigator may utilize participant medical records from non-study care providers to verify whether a participant was infected with SARS-CoV-2. An additional unscheduled, COVID-19 convalescent visit will be preferably conducted within the month after the participant is confirmed with COVID-19. At the convalescent visit, the investigator will seek medical records documenting any treatments and hospitalizations related to COVID-19.

CCI

15.3. MedDRA queries for identifying AESIs

The tables below are MedDRA version specific and may be revised with a new MedDRA version:

Table 15.1 Preferred terms for AESIs which are not pIMDs

Myocarditis	Autoimmune myocarditis
	Eosinophilic myocarditis
	Giant cell myocarditis;
	Hypersensitivity myocarditis
	Immune-mediated myocarditis
	Myocarditis
Pericarditis	Autoimmune pericarditis
	Pericarditis
	Pericarditis adhesive
	Pericarditis constrictive
	Pleuropericarditis
Severe Hypersensitivity	Grade 3 unsolicited AEs under MedDRA SMQ hypersensitivity, narrow search (includes anaphylaxis), with an onset within 24 hours after vaccination

COVID 19 infection will be based on PCR test (there is no MEDDRA query)

Table 15 2 Preferred terms for AESIs which are pIMDs

Event Category	Immune-Mediated Disorder	MedDRA PT	PT Code
Neuroinflammatory disorders	Cranial nerve disorders and inflammations	Anosmia	10002653
		IIIrd nerve paralysis	10021283
		IIIrd nerve paresis	10054202
		IVth nerve paralysis	10023110
		IVth nerve paresis	10054201
		Trigeminal palsy	10049788
		Trigeminal nerve paresis	10068008
		VIth nerve paralysis	10047641
		VIth nerve paresis	10071044
		Facial paralysis	10016062
		Facial paresis	10051267
		Acoustic neuritis	10063162
		Glossopharyngeal nerve paralysis	10051270
		Tongue paralysis	10043972
		Vagus nerve paralysis	10064661
		Vocal cord paralysis	10047674
		Vocal cord paresis	10049234
		XIth nerve paralysis	10048842
		Hypoglossal nerve paralysis	10069450
		Hypoglossal nerve paresis	10067129
		Bulbar palsy	10006542
		Oculofacial paralysis	10030069
		Neuritis cranial	10029244
		Cranial nerve disorder	10061093
		Paresis cranial nerve	10061911
		Cranial nerve paralysis	10061908
		Cranial nerve palsies multiple	10011314
		Optic neuritis	10030942
Multiple sclerosis	Multiple sclerosis	Multiple sclerosis	10028245
		Radiologically isolated syndrome	10079292
		Primary progressive multiple sclerosis	10063401
		Progressive multiple sclerosis	10053395
		Marburg's variant multiple sclerosis	10067067
		Secondary progressive multiple sclerosis	10063400
		Multiple sclerosis relapse	10048393
		Relapsing multiple sclerosis	10080700
		Multiple sclerosis relapse prophylaxis	10070495
		Progressive relapsing multiple sclerosis	10067063
		Relapsing-remitting multiple sclerosis	10063399
		Tumefactive multiple sclerosis	10078556
		Expanded disability status scale score decreased	10071385
		Expanded disability status scale score increased	10071384
Myelitis / Transverse myelitis	Myelitis / Transverse myelitis	Myelitis transverse	10028527
		Myelitis	10028524
		Acute flaccid myelitis	10082097
		Noninfectious myelitis	10071764
Guillain-Barré syndrome	Guillain-Barré syndrome	Guillain-Barré syndrome	10018767
		Miller Fisher syndrome	10049567
Acute disseminated encephalomyelitis and	Acute disseminated encephalomyelitis and	Demyelination	10012305
		Intramyelinic oedema	10083038

Event Category	Immune-Mediated Disorder	MedDRA PT	PT Code
	demyelination (including site specific variants)	Autoimmune demyelinating disease Clinically isolated syndrome Leukoencephalomyelitis Leukoencephalopathy Acute disseminated encephalomyelitis Acute haemorrhagic leukoencephalitis Concentric sclerosis Encephalitis periaxialis diffusa Limbic encephalitis Neuromyelitis optica spectrum disorder Neuromyelitis optica pseudo relapse Autoimmune encephalopathy Bickerstaff's encephalitis Noninfective encephalitis Encephalitis autoimmune Immune-mediated encephalitis Rasmussen encephalitis Encephalitis allergic Encephalitis brain stem Encephalitis haemorrhagic Encephalomyelitis Noninfective encephalomyelitis Encephalitis post immunisation Panencephalitis Encephalitis toxic Chronic lymphocytic inflammation with pontine perivascular enhancement responsive to steroids	10075688 10071068 10048999 10024382 10000709 10058994 10010252 10049020 10078012 10077875 10080353 10075691 10076985 10074712 10072378 10083074 10071141 10056387 10048997 10014589 10014619 10074713 10014602 10056332 10014607 10075197
	Myasthenia gravis	Myasthenia gravis Myasthenia gravis crisis Ocular myasthenia Myasthenic Syndrome	10028417 10062758 10049168 10028424
	Autoimmune / Immune-mediated peripheral neuropathies and plexopathies	Autoimmune neuropathy Immune-mediated neuropathy Neuritis Anti-myelin-associated glycoprotein associated polyneuropathy Subacute inflammatory demyelinating polyneuropathy Chronic inflammatory demyelinating polyradiculoneuropathy Lewis-Sumner syndrome Demyelinating polyneuropathy Polyneuropathy idiopathic progressive Multifocal motor neuropathy Acute motor-sensory axonal neuropathy Acute motor axonal neuropathy Cervical neuritis Mononeuritis Mononeuropathy multiplex Brachial plexopathy Radiculitis brachial Neuralgic amyotrophy	10070439 10078963 10029240 10078324 10081726 10057645 10065580 10061811 10036111 10065579 10076657 10076658 10008293 10027910 10027918 10065417 10037778 10029229
	Narcolepsy	Narcolepsy	10028713

Event Category	Immune-Mediated Disorder	MedDRA PT	PT Code
Musculoskeletal disorders	Systemic lupus erythematosus	Systemic lupus erythematosus	10042945
		SLE arthritis	10040968
		Cutaneous lupus erythematosus	10056509
		Acute cutaneous lupus erythematosus	10057928
		Chronic cutaneous lupus erythematosus	10057929
		Subacute cutaneous lupus erythematosus	10057903
		Lupus cystitis	10074714
		Lupus encephalitis	10025130
		Lupus endocarditis	10058225
		Lupus enteritis	10067738
		Lupus hepatitis	10067737
		Lupus myocarditis	10066391
		Lupus myositis	10079642
		Lupus nephritis	10025140
		Lupus pancreatitis	10067750
		Lupus pleurisy	10073694
		Lupus pneumonitis	10057481
		Lupus-like syndrome	10050551
		Neuropsychiatric lupus	10063663
		Central nervous system lupus	10076328
		Pericarditis lupus	10058149
		Peritonitis lupus	10062898
		Systemic lupus erythematosus rash	10042946
		Systemic lupus erythematosus disease activity index abnormal	10067659
		Systemic lupus erythematosus disease activity index decreased	10067658
		Systemic lupus erythematosus disease activity index increased	10067657
	Systemic Scleroderma (Systemic sclerosis)	Scleroderma	10039710
		Scleroderma renal crisis	10062553
		Scleroderma associated digital ulcer	10073229
		Reynold's syndrome	10070953
		Systemic sclerosis pulmonary	10042954
		Systemic scleroderma	10078638
		Anti-RNA polymerase III antibody increased	10082280
		Anti-RNA polymerase III antibody positive	10082283
		CREST syndrome	10011380
Muscular Autoimmune / Immune-mediated disorders	Muscular Autoimmune / Immune-mediated disorders	Polymyalgia rheumatica	10036099
		Dermatomyositis	10012503
		Polymyositis	10036102
		Autoimmune myositis	10082418
		Immune-mediated myositis	10083073
		Juvenile polymyositis	10076673
		Antisynthetase syndrome	10068801
Rheumatoid arthritis and associated conditions	Rheumatoid arthritis and associated conditions	Rheumatoid arthritis	10039073
		Autoimmune arthritis	10071155
		Immune-mediated arthritis	10083155
		Laryngeal rheumatoid arthritis	10059669
		Rheumatoid lung	10039081
		Rheumatoid scleritis	10067427
		Rheumatic brain disease	10079411

Event Category	Immune-Mediated Disorder	MedDRA PT	PT Code
		Rheumatoid neutrophilic dermatosis	10072362
		Rheumatoid nodule	10048694
		Juvenile idiopathic arthritis	10059176
		Cogan's syndrome	10056667
		Palindromic rheumatism	10033534
		Still's disease	10042061
	Spondyloarthropathies	Arthritis reactive	10003267
		Reiter's syndrome	10038294
		Ankylosing spondylitis	10002556
		Spondylitis	10061371
		Spondyloarthropathy	10051265
		Juvenile spondyloarthritis	10076675
		Enteropathic spondylitis	10076549
		Psoriatic arthropathy	10037162
		Juvenile psoriatic arthritis	10076674
	Relapsing polychondritis	Polychondritis	10065159
	Mixed connective tissue disease	Overlap syndrome	10068786
		Mixed connective tissue disease	10027754
	Gout	Gout	10018627
		Gouty arthritis	10018634
		Gouty tophus	10018641
Gastrointestinal disorders	Inflammatory Bowel disease	Crohn's disease	10011401
		Colitis ulcerative	10009900
		Colitis microscopic	10056979
		Autoimmune colitis	10075761
		Immune-mediated enterocolitis	10078961
		Inflammatory bowel disease	10021972
		Arthritis enteropathic	10003253
		Proctitis ulcerative	10036783
		Autoimmune enteropathy	10081456
	Autoimmune / Immune-mediated pancreatitis	Autoimmune pancreatitis	10069002
		Immune-mediated pancreatitis	10083072
	Celiac disease	Coeliac disease	10009839
Liver disorders	Autoimmune / Immune-mediated hepatobiliary diseases	Autoimmune hepatitis	10003827
		Immune-mediated hepatitis	10078962
		Biliary cirrhosis primary	10004661
		Primary biliary cholangitis	10080429
		Cholangitis sclerosing	10008609
Endocrine and Metabolic disorders	Autoimmune / immune-mediated thyroid diseases	Autoimmune hypothyroidism	10076644
		Immune-mediated hypothyroidism	10083075
		Atrophic thyroiditis	10077172
		Autoimmune thyroiditis	10049046
		Immune-mediated thyroiditis	10083071
		Silent thyroiditis	10079012
		Hashimoto's encephalopathy	10069432
		Hashitoxicosis	10067873
		Basedow's disease	10004161
		Marine Lenhart syndrome	10068828
		Autoimmune thyroid disorder	10079165
	Autoimmune / Immune-mediated endocrinopathy (NOS)	Autoimmune endocrine disorder	10078953
		Immune-mediated endocrinopathy	10078964

Event Category	Immune-Mediated Disorder	MedDRA PT	PT Code
Skin disorders	Diabetes mellitus type I	Type 1 diabetes mellitus	10067584
		Fulminant type 1 diabetes mellitus	10072628
	Polyglandular autoimmune syndrome	Polyglandular autoimmune syndrome type I	10036072
		Polyglandular autoimmune syndrome type II	10036073
		Polyglandular autoimmune syndrome type III	10064115
	Autoimmune hypophysitis	Lymphocytic hypophysitis	10063685
	Addison's disease	Addison's disease	10001130
	Psoriasis	Psoriasis	10037153
	Vitiligo	Vitiligo	10047642
	Erythema nodosum	Erythema nodosum	10015226
Vasculitides	Alopecia areata	Alopecia areata	10001761
	Lichen planus	Lichen planopilaris	10081142
		Lichen planus	10024429
		Acute febrile neutrophilic dermatosis	10000748
		Pemphigus	10034280
	Autoimmune / Immune-mediated bullous skin diseases	Pemphigoid	10034277
		Dermatitis herpetiformis	10012468
		Autoimmune dermatitis	10075689
		Immune-mediated dermatitis	10083156
	Localised Scleroderma	Morphea	10027982
	Vasculitis and vasculitides	Acute haemorrhagic oedema of infancy	10070599
		Administration site vasculitis	10075969
		Anti-neutrophil cytoplasmic antibody positive vasculitis	10050894
		Aortitis	10002921
		Application site vasculitis	10076027
		Arteritis	10003230
		Arteritis coronary	10003232
		Behcet's syndrome	10004213
		Capillaritis	10068406
		Central nervous system vasculitis	10081778
		Cerebral arteritis	10008087
		Chronic pigmented purpura	10072726
		Cutaneous vasculitis	10011686
		Diffuse vasculitis	10012978
		Eosinophilic granulomatosis with polyangiitis	10078117
		Erythema induratum	10015213
		Granulomatosis with polyangiitis	10072579
		Haemorrhagic vasculitis	10071252
		Henoch-Schonlein purpura	10019617
		Henoch-Schonlein purpura nephritis	10069440
		Hypersensitivity vasculitis	10020764
		Injection site vasculitis	10067995
		Kawasaki's disease	10023320
		Langerhans' cell histiocytosis	10069698
		Lupus vasculitis	10058143
		MAGIC syndrome	10078132
		Microscopic polyangiitis	10063344
		Nodular vasculitis	10029491
		Ocular vasculitis	10066926
		Optic ischaemic neuropathy	10030924
		Optic neuropathy	10061323
		Polyarteritis nodosa	10036024

Event Category	Immune-Mediated Disorder	MedDRA PT	PT Code
		Pulmonary vasculitis	10037457
		Renal arteritis	10038373
		Renal vasculitis	10038546
		Retinal vasculitis	10038905
		Rheumatoid vasculitis	10048628
		Segmented hyalinising vasculitis	10067527
		Takayasu's arteritis	10043097
		Temporal arteritis	10043207
		Thromboangiitis obliterans	10043540
		Urticarial vasculitis	10048820
		Vaccination site vasculitis	10076191
		Vascular purpura	10047097
		Vasculitic rash	10047111
		Vasculitic ulcer	10075714
		Vasculitis	10047115
		Vasculitis gastrointestinal	10048319
		Vasculitis necrotising	10047124
Other	Stevens-Johnson syndrome	Stevens-Johnson syndrome	10042033
		Erythema multiforme	10015218
		Toxic epidermal necrolysis	10044223
		SJS-TEN overlap	10083164
	Blood autoimmune / immune-mediated disorders	Autoimmune anaemia	10080243
		Autoimmune haemolytic anaemia	10073785
		Warm type haemolytic anaemia	10047822
		Cold type haemolytic anaemia	10009868
		Coombs positive haemolytic anaemia	10010941
		Evans syndrome	10053873
		Immune thrombocytopenic purpura	10074667
		Thrombocytopenic purpura	10043561
		Thrombotic thrombocytopenic purpura	10043648
		Autoimmune aplastic anaemia	10071576
		Autoimmune neutropenia	10055128
		Autoimmune pancytopenia	10069509
		Immune-mediated pancytopenia	10083004
		Antiphospholipid syndrome	10002817
	Autoimmune / immune-mediated glomerulonephritis	Pernicious anaemia	10034695
		Glomerulonephritis rapidly progressive	10018378
		IgA nephropathy	10021263
		IgM nephropathy	10077209
		C1q nephropathy	10081461
		Glomerulonephritis membranous	10018372
		Glomerulonephritis membranoproliferative	10018370
		Membranous-like glomerulopathy with masked IgG-kappa deposits	10083098
		Mesangioproliferative glomerulonephritis	10066453
		Anti-glomerular basement membrane disease	10081981
		Autoimmune nephritis	10077087
		Immune-mediated nephritis	10083070
		Chronic autoimmune glomerulonephritis	10073016
		Tubulointerstitial nephritis and uveitis syndrome	10069034
	Ocular autoimmune / immune-mediated diseases	Uveitis	10046851
		Vogt-Koyanagi-Harada disease	10082001

Event Category	Immune-Mediated Disorder	MedDRA PT	PT Code
		Ocular pemphigoid	10067776
		Autoimmune retinopathy	10071578
		Acute macular outer retinopathy	10079367
		Autoimmune uveitis	10075690
		Immune-mediated uveitis	10083069
		Autoimmune eye disorder	10081123
	Autoimmune / immune-mediated heart disease	Autoimmune myocarditis	10064539
		Immune-mediated myocarditis	10082606
		Autoimmune pericarditis	10079058
	Sarcoidosis	Sarcoidosis	10039486
		Pulmonary sarcoidosis	10037430
		Neurosarcoidosis	10078011
		Cutaneous sarcoidosis	10011674
		Liver sarcoidosis	10068664
		Muscular sarcoidosis	10028365
		Ocular sarcoidosis	10065700
	Sjögren's syndrome	Sjogren's syndrome	10040767
	Autoimmune lung disease	Idiopathic pulmonary fibrosis	10021240
		Idiopathic interstitial pneumonia	10078268
		Interstitial lung disease	10022611
		Pulmonary fibrosis	10037383
		Autoimmune lung disease	10080701
		Immune-mediated pneumonitis	10082452
	Goodpasture's syndrome	Goodpasture's syndrome	10018620
	Raynaud's phenomenon	Raynaud's phenomenon	10037912

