**Table 2-1 Study Objectives and Endpoints**

Primary Objectives	Primary Endpoints
To evaluate the safety and tolerability of CV0501 at each dose level	
 
Percentage of participants with each solicited local and systemic AE during 7 days after vaccination (ie, the day of study vaccination and 6 subsequent days, Days 1 through 7)
 
Percentage of participants with each abnormal clinical safety laboratory finding for 8 days after study vaccination
 
Percentage of participants with unsolicited AEs for 28 days after study vaccination
 
Percentage of participants with MAAEs, AESIs and SAEs from study vaccination through the end of the study (for 180 days after the study vaccine administration), each summarized separately
 

Secondary Objectives	Secondary Endpoints
To evaluate neutralizing Ab titers against SARS-CoV-2 WT, Omicron, and Delta variants following CV0501 booster vaccination in adult participants	
 
GMTs of neutralizing Ab against pseudovirus bearing S protein from SARS-CoV-2 WT, Omicron, and Delta variants at each collection timepoint
 
GMI from baseline of neutralizing Ab titers against pseudovirus bearing S protein from SARS-CoV-2 WT, Omicron, and Delta variants at each collection time point
 

To describe seroresponse to CV0501 based on neutralizing Ab titers against pseudoviruses bearing S protein from SARS-CoV-2 WT, Omicron, and Delta variants	
 
Seroresponse rate 28 days after the booster dose (Day 29), based on neutralizing Ab titers against pseudoviruses bearing S protein from SARS-CoV-2 WT, Omicron, and Delta variants at each collection timepoint, with seroresponse defined as postboost titers <math>\geq 4\times</math> preboost titers.
 

Tertiary Objectives	Tertiary Endpoints:
CCI	

GlaxoSmithKline Biologicals SA

CV0501 Vaccine

Protocol 218595 (CV2 SARS-COV2-012 BST) Amendment 2

26 Jul 2022

CCI

[figure not shown]

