### **6.1.1.4      Adverse Events of Special Interest**

An AESI (serious or nonserious) is defined as an AE or SAE of scientific and medical concern specific to the sponsor's product or program, for which ongoing monitoring and rapid communication by the investigator to the sponsor could be appropriate (ICH E2F; CIOMS VI).

For this study, prespecified AESIs will include the following events:

- Virologically confirmed COVID-19 (see [Section 6.4](#) for definition)
- Potential immune-mediated disorders ([Section 13.4](#))
- Anaphylaxis or severe hypersensitivity within 24 hours after study vaccine administration
- Myocarditis
- Pericarditis

Refer to [Section 6.1.1.3.1](#) for reporting AESIs.

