- Grade 3 (Severe): An AE that prevents normal, everyday activities. In adults, such an AE would, for example, prevent attendance at work and would necessitate the administration of corrective therapy.

An AE that is assessed as Grade 3 (severe) should not be confused with an SAE. Grade 3 is a category used for rating the intensity of an event; and both AEs and SAEs can be assessed as Grade 3. An event is defined as “serious” when it meets the definition of an SAE ([Section 6.1.1.1.2](#)).

Refer to [Section 6.1.2](#) for grading of laboratory-associated AEs.

Changes in the severity of an AE should be documented to allow an assessment of the duration of the event at each level of intensity. Adverse events characterized as intermittent do not require documentation of onset and duration of each episode.

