9.1.2 Severity of Adverse Event

The severity of AEs (mild, moderate, severe) will be captured on the eCRF. Adverse events (unsolicited AEs, solicited AEs, and SAEs) will be summarized including the number of participants and percentages by dose group, study vaccine, as well as by SOC, PT, and severity. If the severity is missing, then a “missing” severity category will be included in the summary. A participant with 2 or more AEs within the same SOC or PT level but different severity will be counted only once at the most severe level.

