9.1.6 Adverse Events of Special Interest

An AESI (serious or nonserious) is defined as an AE or SAE of scientific and medical concern specific to the sponsor's product or program, for which ongoing monitoring and rapid communication by the investigator to the sponsor could be appropriate (ICH E2F; CIOMS VI).

Adverse events of special interest will include the following events:

- Virologically confirmed Covid-19 (see protocol section 6.4 for definitions)

- Potential immune-mediated disorders (see protocol section 13.4 for definitions)
- Anaphylaxis or severe hypersensitivity within 24 hours after study vaccine administration
- Myocarditis
- Pericarditis

AESIs will be identified using MedDRA queries and Investigator identification as per eCRF. Refer to appendix [15.3. MedDRA queries for identifying AESIs](#) for details on these queries.

The percentage of participants with AESIs with onset date within day 1-28 and within day 1-180, identified by either the investigator or by MedDRA queries, will be provided by SOC and PT for each dose group.

Similarly, AESIs that are related to COVID-19 will be presented in a separate listing by age group, dose group and participant number.

AESIs will be reported until exit from study (up to day 180 after the study vaccine administration, day 1-180).

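### The SAP's hypersensitivity query retrieves anaphylaxis only at Grade 3, although the AESI definition it implements sets no grade for anaphylaxis

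*SAP*

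**What the plan says.** The protocol's section on adverse events of special interest (6.1.1.1.4 in its table of contents) lists "Anaphylaxis or severe hypersensitivity within 24 hours after study vaccine administration". The synopsis, under Safety Assessments, gives the same definition, and SAP Section 9.1.6 repeats it. AESI status does not depend on seriousness: "An AESI (serious or nonserious) is defined as an AE or SAE of scientific and medical concern".

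The SAP puts the definition into practice in two ways. Section 9.1.6 states: "AESIs will be identified using MedDRA queries and Investigator identification as per eCRF". The AESI table then counts events "identified by either the investigator or by MedDRA queries".

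The query side is in SAP Section 15.3. Table 15.1 has one row for this AESI, labelled as severe hypersensitivity, and its content is "Grade 3 unsolicited AEs under MedDRA SMQ hypersensitivity, narrow search (includes anaphylaxis), with an onset within 24 hours after vaccination". Neither Table 15.1 nor the pIMD list in Table 15.2 has a separate row or preferred term for anaphylaxis.

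AESIs belong to a primary endpoint in Protocol Table 2-1: "Percentage of participants with MAAEs, AESIs and SAEs from study vaccination through the end of the study".

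**The concern.** In the definition, the word severe stands before hypersensitivity and after anaphylaxis. On the natural reading, anaphylaxis is an AESI as a diagnosis, and only other hypersensitivity has to be severe. The query row puts one Grade 3 condition on the whole search and says in its parenthesis that anaphylaxis is inside that search. So the query tests anaphylaxis against a condition that the definition does not contain.

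This row is also the exception in its table. The myocarditis and pericarditis rows list preferred terms with no grade condition.

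At stake is complete ascertainment of an event that Protocol Section 1.2 names among the important potential risks. When two routes are combined so that either is enough, each adds only what the other missed. The query therefore contributes exactly when there is no investigator flag, and for anaphylaxis below Grade 3 it contributes nothing.

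**Working it through.** The plan gives no figure on this point and no arithmetic applies. The check sets the definition against the query and follows each type of event through to the AESI table.

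**Inputs**

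- Definition (Protocol AESI section, synopsis, SAP 9.1.6): anaphylaxis, or hypersensitivity that is severe; onset within 24 hours.
- Query (SAP Table 15.1): Grade 3, and unsolicited, and in the narrow hypersensitivity SMQ, and onset within 24 hours.
- Combination rule (SAP 9.1.6): investigator flag or query.
- Grade and seriousness are separate (Protocol, Assessment of Intensity): "Grade 3 is a category used for rating the intensity of an event; and both AEs and SAEs can be assessed as Grade 3". Nothing in the documents requires anaphylaxis to be graded 3.
- Severity scale (SAP 9.1.2): "The severity of AEs (mild, moderate, severe) will be captured on the eCRF". The same section provides a category for missing severity, so an ungraded event is foreseen, and it cannot meet a Grade 3 condition.

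**Cases, all unsolicited with onset within 24 hours and coded to a narrow-search term**

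| Event | AESI by definition | Retrieved by query | In AESI table |
|---|---|---|---|
| Anaphylaxis, Grade 3 | yes | yes | yes |
| Anaphylaxis, below Grade 3 or ungraded, flagged | yes | no | yes, by the flag |
| Anaphylaxis, below Grade 3 or ungraded, not flagged | yes | no | **no** |
| Other hypersensitivity, Grade 3 | yes | yes | yes |
| Other hypersensitivity, Grade 1 or 2, not flagged | no | no | no |

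Definition and AESI table disagree in one row only, the third. For hypersensitivity other than anaphylaxis, the Grade 3 condition matches the definition and should stay.

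**Where a third-row event still appears.** It is in the unsolicited AE summary by SOC and PT for each dose group (SAP 9.1.5), which includes a column for any grade. It is in the MAAE tables if it led to medical attention outside scheduled study visits (SAP 9.1.8). It is in the SAE tables if it met a seriousness criterion (SAP 9.1.7). Only its classification as an AESI is missing.

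**The case against.** The case against has real weight on how often this could happen.

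- Investigators grade unsolicited events by the greatest intensity reached (Protocol, Assessment of Intensity), so a reaction that settles fast is not graded lower for that reason. The Grade 3 description gives a need for corrective therapy as an example, which pulls treated reactions towards Grade 3. Grade 1 is for events that are easily tolerated. An anaphylaxis below Grade 3 is therefore a narrow category, most plausibly Grade 2 or ungraded. It is not empty, because grading rests on clinical judgment.
- A missing flag is unlikely. Participants are observed for at least 60 minutes and told to contact the site at once about a possible hypersensitivity reaction within a day (Protocol Section 1.2). Anaphylaxis is a named AESI, and sites must report AESIs within 24 hours of learning of them.
- The SAP does not call the query a back-up to the flag. A query limited to severe events, next to investigator identification, would be a permissible design, and the row's label points that way. But the parenthesis says that the row covers anaphylaxis, and the SAP nowhere says that milder cases rest on the flag alone.
- Severe could be read as covering anaphylaxis too. That is possible but less natural, because anaphylaxis comes before the adjective and is listed separately.

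These points limit the size. They do not remove the mismatch: where no flag exists, the rule that accepts either route has nothing to count.

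Two stronger readings are tempting and should be resisted. A reader might infer that anaphylaxis below Grade 3 drops out of the AESI analysis. It does not, because a flagged case counts at any grade. A reader might also size the defect as one participant's share of a group, such as 1/30 = 3.3 percentage points in a full Part A cohort or 1/15 = 6.7 in a Part B cohort. That is only the weight of one person in the denominator. It says nothing about how often an event is both unflagged and below Grade 3 or ungraded, so it is not an estimate of bias.

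**Conclusion.** The mismatch holds. The query in SAP Table 15.1 is narrower than the AESI definition in the protocol and in the SAP's own Section 9.1.6, because its Grade 3 condition extends to anaphylaxis.

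The effect is confined to anaphylaxis within 24 hours that is below Grade 3 or ungraded and that the investigator did not flag. The documents give no basis for estimating how many such events there would be; the safeguards around vaccination suggest few. The event would still be visible in other safety tables, and the query has no stated role in site reporting or in the study holding rules.

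The conclusion assumes that severe qualifies hypersensitivity only and that the table row will be programmed as written. It is a minor correction, worth making because it concerns a component of a primary safety endpoint.

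**What to change.** Reconcile Table 15.1 with the protocol's AESI definition and SAP Section 9.1.6 by splitting the row in two:

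- (a) anaphylaxis terms, any grade or missing grade, onset within 24 hours after vaccination;
- (b) all other terms in the narrow hypersensitivity search, Grade 3, onset within 24 hours after vaccination.

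The preferred terms for (a) should be listed, as they are for myocarditis and pericarditis. If the sponsor prefers to keep a single Grade 3 row, the SAP should at least say that anaphylaxis below Grade 3 or without a grade is identified by the investigator alone.

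The cost is one added line in a SAP appendix and the matching line of programming. It needs no new data and no protocol amendment, and changes nothing in the clinical management of participants.
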